10.3.2 Subject-specific vs. population-averaged model

We chose to employ a subject-specific model as it allows to model explicitly different sources of variability and makes it easier to specify the covariance structure. Under the identity link with Gaussian errors, the model coefficients have both a subject-specific and a population-averaged interpretation. Further, if interdependence between the participants attending the same group therapy sessions has to be incorporated into the model, this could be easily done using a subject-specific model.

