2.0 STUDY SYNOPSIS

STUDY OBJECTIVES: The primary objective of this protocol is to evaluate the degree to which a combined group and individual 12-Step facilitative intervention, Stimulant Abuser Groups to Engage in 12-Step (STAGE-12), improves substance-related outcomes compared to treatment as usual (TAU) without STAGE-12 among stimulant abusers. For this protocol, STAGE-12 will be integrated into treatment as usual. The primary objective is to evaluate reduction in percent of days of stimulant use as measured by self-report. Secondary objectives include evaluating reduction in percent days of use of other substances, the degree to which STAGE-12 increases involvement in 12-step activities and attendance at 12-step meetings, and the extent to which such 12-step involvement and meeting attendance mediate substance use outcomes.

STUDY DESIGN: This is a randomized, 2-group design comparing STAGE-12 integrated into TAU (STAGE-12) to TAU without STAGE-12 (TAU) for stimulant abusers receiving formal substance abuse treatment in participating community-based treatment programs (CTPs). For the purposes of this study, the STAGE-12 sessions will replace 8 sessions (3 individual and 5 group sessions) from TAU during the course of the intervention period, which may range from 5 up to 8 weeks. Eligible, consented stimulant abusers entering treatment at participating CTPs will be assigned randomly within site through a centralized randomization procedure to STAGE-12 or TAU and will be stratified by participants' court-mandated for treatment versus not court-mandated. Assessments will be conducted as indicated in Table 1 at baseline, weeks 2, 4, and 8. Follow-up assessment will occur at 3 and 6 months after randomization.

STUDY POPULATION: A total of approximately 400 stimulant users seeking formal treatment, recruited from approximately 10 CTPs, will be randomized to STAGE-12 or TAU. Each CTP will enroll approximately 40-50 participants, with a target of 20-25 per CTP in each treatment condition. Eligible CTPs and counselors will be assessed to characterize their general treatment philosophy/orientation.

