The five group sessions follow a similar format beginning with a "check-in" in which members introduce themselves, report on their homework related to AA, NA, CA, or CMA participation, and any strong desires or cravings to use drugs or alcohol. The remainder of the session focuses on an interactive discussion of the content of the sessions, a summary of key "take-home" messages, and the assignment of homework between sessions. There is no set order in which participants are required to attend sessions; that is, session content is independent and there is no prerequisite of attending one session before the next. This allows for rolling admission to groups. When surveyed about their preference of closed-admission, cohort-based groups versus open, rolling admission groups, CTPs overwhelmingly (95.4%) endorsed the use of rolling admission.

Rolling admission will be used in the group sessions, so that a minimum membership may be maintained in each session. Participants assigned to the STAGE-12 intervention will be able to join the group at any session, following attendance at their first individual therapy session. In order to facilitate the rolling admissions to groups, two of the core sessions from the TSF for Drug Abuse and Dependence manual will be delivered as individual sessions. These include the introduction/assessment session and the termination session. The content of these sessions does not lend itself to rolling admissions and seems appropriate to be delivered individually. Each group will have a minimum of 2 and a maximum of 15 participants per session.

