6.4 Counselors/Staffing

Two counselors and one supervisor will be selected at each CTP to provide the STAGE-12 intervention. The counselors will each provide the STAGE-12 intervention based on meeting scheduling and caseload, and may also cover TAU sessions as assigned by the CTP. The supervisor will provide fidelity monitoring to the intervention and provide back-up support for group sessions in the event a counselor is unavailable for a scheduled session. All other staff at the CTP will provide the standard treatment.

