10.6 Sample Size and Power Calculations

[figure not shown]
The sample size required for detecting a time by group interaction is estimated using the formulas due to Hedeker et al. (Hedeker, Gibbons, Waternaux, 1999). The following assumptions are employed. Four replicate, continuous, approximately normally distributed outcome (Percent of Days of Drug Use) measurements are to be obtained at 4, 8, 13 and 26 weeks (the baseline value is to be entered as a covariate). A two-sided type-I error rate (alpha) is set at 0.05 and power (1-beta) is assumed as 80%.

The expected effect size was determined by incorporating information from two sources. First, in the Brown, Serganian, et al. (2002) study of group-based TSF versus an active comparison therapy (relapse prevention [RP]), the standard deviation for "days of use in previous 90 days" was 24 days in the TSF group and 17.7 days in the RP group, giving a pooled estimate of the standard deviation of 21.3 days, or 23.7% of days of substance use over the 6-month assessment window. Second, clinicians and program directors from multiple CTPs in the CTN were asked about what they viewed as a potentially clinically meaningful difference between their TAU and an experimental treatment such as TSF. They indicated that a 10% difference, on average, in percent days of use between TAU and a new therapy would be clinically meaningful. A 10% difference divided by a standard deviation of 23.7% gives a standardized effect size of 10/23.7 = 0.42. Effects of this magnitude are in the 'small' to 'medium' range in the power analysis literature (Cohen, 1983). Based on or anticipated ability to track, follow, and assess participants at the follow-up points, a total retention rate of 70% for the duration of the trial was assumed, with the dropout rate occurring evenly over the 4 post baseline points is assumed; however, it should be noted that the follow-up rates in the Brown, Serganian, et al. (2002) was only about 50% at the 6-month follow-up. Compound symmetry with a correlation parameter of 0.5 is also assumed; however, there is no information available on the correlation pattern between observations.

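### The primary model has no term for shared STAGE-12 counselors and groups; if the resulting slope correlation is above zero, the standard error of the treatment effect is too small

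*Protocol*

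**What the plan says.** Section 10.3.1 gives the primary analysis as a two-level linear model for percent of days of stimulant use. Each participant's slope is a site term, plus a constant STAGE-12 effect (alpha_1), plus a participant deviation. These deviations are assumed independent. The site terms for level and slope do not differ by arm. There is no counselor, therapy-group or site-by-arm term.

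Section 10.3.2 is the only place that mentions correlation between participants: "if interdependence between the participants attending the same group therapy sessions has to be incorporated into the model, this could be easily done". It does not say what would show that this is needed, which term would be added, or when the decision would be taken.

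The delivery of STAGE-12 is described elsewhere:
- Section 2.0: "Each CTP will enroll approximately 40-50 participants, with a target of 20-25 per CTP in each treatment condition".
- Section 6.4: "Two counselors and one supervisor will be selected at each CTP to provide the STAGE-12 intervention". Section 5.1.2.1 says at least two counselors.
- Section 6.2.2: "Rolling admission will be used in the group sessions, so that a minimum membership may be maintained in each session". Sessions hold 2 to 15 people.
- Sections 5.1.3 and 6.2.1: five of the eight STAGE-12 sessions are group sessions.

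Section 10.6 bases the sample size on independent participants. On the effect size it says that a 10-point difference "gives a standardized effect size of 10/23.7 = 0.42". On repeated measures it says "Compound symmetry with a correlation parameter of 0.5 is also assumed", which concerns correlation within a participant and not between participants. The blinded check in section 10.7 looks at the outcome variance and its consistency over time, not at clustering.

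**The concern.** Participants who share a counselor or sit in the same sessions may change in similar ways. The protocol's rationale for the group format in section 3.7.2 relies on members learning from and supporting one another, and sections 5.3.2 and 9.2 expect counselors' backgrounds to vary. A counselor or group effect in one arm at a site cannot go into the site terms, because those are shared by both arms. It goes into the participant deviations, which the model counts as independent pieces of information. The model-based standard error of alpha_1 then omits part of the real sampling variation.

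What is at stake is the primary p-value and confidence interval. There is a second consequence: because section 10.3.2 leaves the choice open, whether to add a clustering term could be decided after the results are known, and that choice can change the primary conclusion.

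**Working it through.** **The plan's own figures.** The SD is 21.3/90 = 23.7 percentage points, and 10/23.7 = 0.42; both reproduce. The stated power of about 85% at 200 per arm (effect size 0.42, rho 0.5, 30% attrition) does not follow from the protocol's table. The row for effect size 0.4, 30% attrition and rho 0.5 gives 165 per arm for 80% power. Scaling from it:

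- (1.960 + 0.842) × (0.42/0.40) × sqrt(200/165) = 3.239
- power = Phi(3.239 − 1.960) = Phi(1.279) = 90%, or 87% with effect size 0.4.

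The 165 itself could not be confirmed, because section 10.6 states neither the contrast nor the shape of the effect over time. I do not call it wrong. Neither figure allows for clustering.

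**Inputs for the clustering check.** From the protocol: two-sided alpha 0.05, stated power 85%, 20-25 participants per arm and site, two STAGE-12 counselors per site, about 10 sites. Assumed, because the protocol gives nothing: an ICC of 0.01 to 0.05, meaning the share of the within-site variance of participants' estimated slopes that is common to a delivery unit. Cluster size m is 10 (20 participants over two counselors) or 20 (the whole site arm as one cluster).

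**Formulas, clustering in STAGE-12 only.**
- Design effect in that arm: D = 1 + (m − 1) × ICC
- Variance ratio of the arm difference: V = (1 + D)/2
- Actual type I error of the model as written: 2 × Phi(−1.96/sqrt(V))
- Power once the standard error is correct: Phi(k/sqrt(V) − 1.96), with k = 1.960 + 1.036 = 2.996 for a start of 85%, or 3.239 for a start of 90%

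| m | ICC | D | V | SE factor | Type I error | Power from 85% | Power from 90% |
|---|---|---|---|---|---|---|---|
| 10 | 0.01 | 1.09 | 1.045 | 1.02 | 5.5% | 83% | 89% |
| 10 | 0.05 | 1.45 | 1.225 | 1.11 | 7.7% | 77% | 83% |
| 20 | 0.01 | 1.19 | 1.095 | 1.05 | 6.1% | 82% | 87% |
| 20 | 0.05 | 1.95 | 1.475 | 1.21 | 10.7% | 69% | 76% |

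At ICC 0 nothing changes.

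**Clustering in both arms.** V becomes D. At m = 20 and ICC 0.05, V = 1.95, the SE factor is 1.40 and type I error is about 16%.

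**Simulation check.** Ten sites, 20 per arm and site, site effects in the analysis, 20,000 runs per setting. With clustering in STAGE-12 only, type I error at ICC 0.05 was 7.9% (m = 10) and 10.8% (m = 20). With both arms clustered at m = 20 it was 17.0%. At ICC 0 it was 5.1% for both cluster sizes.

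**The case against.** A reader might infer three stronger claims that the protocol does not support.

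- **That the standard error is too small as a matter of fact.** This needs a positive slope ICC beyond site, and none is documented. The site terms already absorb whatever is common to both arms at a site. STAGE-12 replaces only eight sessions in programs of 5-15 hours a week, and the slope runs to 26 weeks although the sessions end by week 8. The ICC could be small.
- **That each site has a single overlapping group of 20-25.** Section 6.4 divides the work between counselors by scheduling and caseload. Sessions hold 2-15 people, up to 6 of whom may be non-participants (section 6.2.4). Entry is rolling, and STAGE-12 is delivered over 5 to 8 weeks, so people enrolled far apart need never meet. A cluster of 20 is near the upper end; 10 is at least as plausible.
- **That the trial is underpowered.** Starting from the 90% implied by the table, m = 10 and ICC 0.05 still leaves 83%, above the planned 80%.

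Two further objections bear on the remedy. TAU also has counselors and groups, and STAGE-12 counselors may cover TAU sessions (section 6.4), so a term for STAGE-12 alone could leave correlation unmodelled. And no section shows that each participant's counselor or group is recorded; section 5.4.3.5.4 describes the tracking form as capturing sessions and hours.

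It can also be said that this belongs in a separate statistical analysis plan, since section 10.3.2 chose a model class that can take such a term. That does not remove the point. The protocol writes out the primary model and its independence assumption, so the choice is already fixed, and fixed without the term.

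What stands is the missing term, the open conditional and the absence of any clustering allowance in section 10.6. TAU clustering is no defense of the model: it makes the understatement larger.

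**Conclusion.** The concern holds in conditional form. As written, the primary analysis gives too small a standard error for alpha_1, and a type I error above 5%, whenever the slope ICC from shared counselors or groups exceeds 0. For an assumed ICC of 0.01-0.05 in the STAGE-12 arm only, type I error is about 5.5-7.7% with clusters of 10 and 6.1-10.7% with clusters of 20. Equal clustering in both arms at ICC 0.05 and m = 20 gives about 16%.

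The stated 85% power would become 83-77% (m = 10) or 82-69% (m = 20). The power figures are the weaker part, because 85% does not itself follow from the table. All of these sizes rest on the assumed ICC and cluster sizes; the missing term and the open conditional do not.

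**What to change.** Before unblinding, replace the conditional sentence in section 10.3.2 with a stated random effect on the slope for the delivery unit:

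- Use counselor or group if that identity is recorded for each participant. Otherwise use site-by-arm, which needs no new data because site and arm are known from randomization.
- State how TAU groups, and counselors who work in both arms, are handled.
- Use small-sample degrees of freedom, for example Kenward-Roger.
- In section 10.6, show power over a range of ICC and cluster size instead of one figure that assumes no clustering, starting from a base that agrees with the table.

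The cost is a wider interval, one or more extra variance components, and a lower stated power. The loss of degrees of freedom is real. If the unit is site, with about 10 sites, they fall towards 9 and the critical value rises from 1.96 to 2.26. At m = 20 and ICC 0.05, starting from 85%, power is then about 60% rather than 69%. If the ICC turns out near zero, the price is some lost precision and degrees of freedom.

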10.4 Secondary Outcomes

Key secondary endpoints are listed below in order of priority. No adjustment for multiplicity of the comparisons will be made and any statistically significant findings will be treated as exploratory.

- 1. Substances use other than stimulants (including alcohol) derived from Substance Use Calendar
- 2. 12-step meeting attendance derived from Substance Use Calendar
- 3. 12-step meeting attendance derived from Self-Help Activities Questionnaire
- 4. Involvement in 12-step activities derived from Self-Help Activities Questionnaire
- 5. Urine drug screen
- 6. Alcohol and Drug Use Composite Scores derived from the ASI

Other secondary endpoints should be considered as exploratory.

The following data analytic methods will be used to test hypotheses related to these secondary endpoints.

- a. Hierarchical linear modeling will be used to assess the following endpoints:
 - 1. % of days of non-stimulant use over assessment window (via Substance Use Calendar)
 - 2. % of days of 12-step meeting attendance
 - 3. Involvement in 12-step activities
 - 4. ASI Drug and Alcohol composite Scores
 - 5. Spirituality derived from the Spiritual Involvement and Beliefs Scale
 - 6. Perceived barriers to 12-step involvement derived from the Survey of Readiness for Alcoholics Anonymous Participation
- b. The proportional mean model will be used to assess these endpoints:
 - 1. Positive drug screen from urinalysis

10.4.1 Substance Use Outcomes

10.4.1.1 Objective

To evaluate the degree to which a brief, combined group-plus-individually delivered 12-step facilitative intervention, integrated into treatment as usual, reduces the percent of days of use of non-stimulant drugs for participants with stimulant abuse or dependence disorders compared to TAU

10.4.1.1.1 Hypothesis

STAGE-12 will result in less non-stimulant substance use, as indicated by percent days of use on the Substance Use calendar, than TAU.

The outcome variable will be percent of days of non-stimulant use over the assessment window, based on Substance Use Calendar alone and assessed at baseline, weeks 4, 8/end of treatment, 3 months and 6 months. The data will be analyzed using a hierarchical linear model similar to the model for the primary outcome. Let α_{NS} denote the effect of the STAGE-12 treatment in the Level-2 model. The hypotheses H₀: α_{NS} =0 vs. H₁: α_{NS} \neq 0 will be evaluated and rejection of the null hypothesis with α_1 < 0 would indicate that STAGE-12 treatment reduces percent of days of substance use compared to TAU.

10.4.1.1.2 Hypothesis

STAGE-12 will result in fewer positive drug screens/urinalyses than TAU.

The outcome variable will be positive drug screen (yes/no) measured at baseline, weeks 4, 8/end of treatment, 3 months and 6 months. The data will be analyzed using the proportional mean model for recurrent events (Lin et al., 2000):

$$\mu_Z(t) = E\{N_i(t) | Z_i\} = \exp(\lambda_D Z_i)\mu_0(t),$$

where Z_i = 0 if the participant belongs to TAU group and Z_i = 1 if the participant belongs to STAGE-12 group; $N_i(t)$ is the total number of positive drug screen results for participant i at the time of assessment t; λ_D is the effect of the STAGE-12 treatment. The advantage of the proportional mean model is that it does not assume the nature of the influence of prior events on the future recurrence. The following statistical hypotheses will be assessed: H_0 : λ_D =0 vs. H_1 : $\lambda_D \neq 0$. Rejection of the null hypothesis with λ_D < 0 would indicate that STAGE-12 treatment results in fewer positive drug screens than TAU. The analysis will be performed using PROC PHREG with TIE=DISCRETE option for handling ties event times and COV(AGGREGATE) option to request the robust sandwich covariate matrix estimate.

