5.1.2.2 Participant Randomization

Participants will be randomized after completing the initial eligibility screen, baseline data collection, and a check to be sure that they are still attending outpatient treatment in the participating CTP. Participants will be randomized to one of the two treatment conditions (TAU or STAGE-12) after

completion of baseline assessments. The randomization process will be conducted in a centralized process through the Data and Statistics Center (DSC). Randomization will be stratified by site and by participants court-mandated to treatment vs. participants not court mandated to treatment.

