5.4.3.1 Substance Use Indices

5.4.3.1.1 Urine Drug Screen

Although the Substance Use Calendar that will be used to assess days of drug use has demonstrated reliability and validity when compared against both collateral reports of drug use and urine toxicology results (Ehrman and Robbins 1994; Fals-Stewart, O'Farrell et al. 2000), and there is considerable evidence supporting the validity of self-reported substance abuse by drug users (Brown, Kranzler et al. 1992; Darke 1998), there continue to be concerns about the veracity of such self-reports (Magura and Kang 1996). Therefore, urine will be tested for the presence of cocaine, opiates, cannabis, benzodiazepines, methamphetamines, and amphetamines. Urine samples will be collected at the baseline interview, weeks 4 and 8 during the active intervention phase, and at each of the follow-up assessments.

Zanis et al (Zanis et al.1994) indicated that their results suggest that self-reports of drug use are more inclusive estimates of use than even weekly urinalysis. However, they as well as others (e.g., Fals-Stewart, et al., 2000; Del Boca and Noll, 2000) indicate that such self-reports were collected in the context of a setting in which urine results were also being collected and recommend continued use of urine collection. However, they do not necessarily advocate that urine results be viewed as a "gold standard." Rather, they point to the fact that one of the important conditions for obtaining valid selfreports of substance use is informing participants that their self-reports will be validated against an objective standard such as urines. This may enhance the accuracy of the participants' self-reports via a bogus pipeline effect (Jones and Sigall, 1970). Such effects occur when research participants provide information under conditions where they are led to believe that objective, external validation of their responses is available. The possibility that inaccuracies can be detected is hypothesized to increase the validity of verbal report data (Del Boca and Noll, 2000). This hypothesis was supported by the results of Hamid and colleagues (Harnid, Deren et al.1999), who found that the agreement between self-reported drug use and urine test results was significantly higher when the urine collection occurred prior to the self-report associated with timing of urine testing. Thus, urine screens will be conducted prior to the Substance Use Calendar to maximize the validity of the self-reports.

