10.4.4.1.5 Hypothesis

Individuals with higher levels of readiness to change their substance use behaviors are more likely to attend 12-step meetings and engage in 12-step activities than are those with lower levels of readiness to change.

The outcome variable will be 12-step meetings meeting attendance (yes/no). For each of the hypotheses listed above the data will be analyzed using the proportional mean model for recurrent events similar to the model for mean number of positive drug screens in 10.4.1.1.2. In this model, variable Z_i will be an indicator of a particular group of interest (e.g., ethnic minorities vs. Caucasian in the analysis for 1.3.4.1)

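### The urine analysis counts the pre-randomisation baseline screen as an outcome, which pulls the treatment ratio toward 1, and it has no term for screens actually taken

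*Protocol*

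**What the plan says.** Section 10.4.1.1.2 sets the outcome and its times: "The outcome variable will be positive drug screen (yes/no) measured at baseline, weeks 4, 8/end of treatment, 3 months and 6 months". It applies a proportional mean model for recurrent events, in which the mean count in an arm is exp(λ_D Z_i) times a baseline mean function μ_0(t). The counted quantity N_i(t) "is the total number of positive drug screen results for participant i at the time of assessment t". The only covariate is the arm indicator, which is 0 "if the participant belongs to TAU group and Z_i = 1 if the participant belongs to STAGE-12 group". The section also names the software procedure, the option for ties and the robust variance. It gives no rule for missed screens, at-risk status or censoring.

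Section 5.1.2.2 fixes the order of events: "Participants will be randomized after completing the initial eligibility screen, baseline data collection". Section 5.4.3.1.1 gives the sampling schedule: "Urine samples will be collected at the baseline interview, weeks 4 and 8 during the active intervention phase, and at each of the follow-up assessments". That is one screen before randomisation and four after it.

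The primary model in Section 10.3.1 is built differently. It indexes post-baseline assessments, represents baseline through the intercept, and includes site and court mandate. The likelihood argument in Section 10.5 is made for the hierarchical model only. Section 10.4 ranks the urine screen fifth of six key secondary endpoints and treats significant findings among them as exploratory.

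**The concern.** Read plainly, a positive baseline screen is already in N_i(t) when follow-up starts. At that time the expected ratio between randomised arms is 1, whatever the treatment does later. The model nevertheless fits one ratio across all five times, with no term separating before from after. If STAGE-12 works, the fitted ratio is an average of a structural 1 and the real effect. The report would then understate the effect and could miss it.

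The second issue is what the count does with an absent result. A negative screen and a missed screen both add zero to N_i(t). Unless the participant is removed from the risk set at that visit, the two cannot be told apart, and the arm with more intermittent misses looks better.

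**Working it through.** The protocol states no positivity rate, event count or power for urine, so there is no figure to reproduce. The rates below are assumptions. The document supplies the five times, the count, the single covariate and about 200 participants per arm.

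**Step 1: baseline in the count, complete data.** Let p0 be positivity at baseline (both arms), pC positivity at each of four follow-up visits in TAU, and RR the true post-randomisation ratio. With everyone at risk throughout, the fitted ratio is the ratio of mean total counts:

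(p0 + 4·pC·RR) / (p0 + 4·pC)

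With p0 = 0.40, pC = 0.30 and 20% positive under STAGE-12:
- Follow-up only: (4 × 0.20)/(4 × 0.30) = 0.80/1.20 = 0.667.
- Baseline counted: (0.40 + 0.80)/(0.40 + 1.20) = 1.20/1.60 = 0.75.

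The cumulative ratio is not constant over time, as the model requires:
- baseline: 0.40/0.40 = 1
- week 4: 0.60/0.70 = 0.86
- week 8: 0.80/1.00 = 0.80
- month 3: 1.00/1.30 = 0.77
- month 6: 1.20/1.60 = 0.75

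For RR = 0.70 over a range of assumed rates:

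| p0 | pC | Fitted ratio | Loss of log effect |
|---|---|---|---|
| 0.3 | 0.4 | 1.42/1.90 = 0.747 | 18% |
| 0.5 | 0.3 | 1.34/1.70 = 0.788 | 33% |
| 0.7 | 0.2 | 1.26/1.50 = 0.840 | 51% |

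**Step 2: power and type I error.** The estimator was simulated with robust variance, 200 per arm, latent within-person correlation 0.5 and 1,000 to 2,000 replicates. Ties were handled by the Breslow method, not the planned DISCRETE option, so the results describe the model's mean ratio and not the exact planned output.
- Central case (p0 = 0.5, pC = 0.3, RR = 0.70): power 69% with baseline counted, 86% without.
- Across the range of rates: 45–87% with baseline counted, 64–96% without.
- No true effect: rejection 4.0% with baseline, 5.2% without.

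**Step 3: missed screens, no true effect, follow-up visits only.** If everyone stays at risk and screens are missed at random at rates m0 (TAU) and m1 (STAGE-12), positivity cancels and the ratio is (1 − m1)/(1 − m0). For 10% against 30% missed this is 0.70/0.90 = 0.78. Simulated results:

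| Missingness | Handling | Ratio | Rejection |
|---|---|---|---|
| Intermittent, 10% vs 30% | all at risk to month 6 | 0.77 | 60% |
| Intermittent, 10% vs 30% | censored after last attended visit | 0.85 | 27% |
| Dropout, 20% vs 40% | all at risk to month 6 | 0.86 | 24% |
| Dropout, 20% vs 40%, unrelated to use | censored after last attended visit | 1.00 | 6% |
| Equal in both arms | as above | about 1.00 | 4–5% |
| 10% vs 30% missed | at risk only at screens taken | 1.00 | about 6% |

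**The case against.** The listing of baseline is phrasing that recurs across the secondary outcomes. Whether a time-zero positive enters the fit depends on a data set-up the protocol does not describe. That is fair, but the section defines the count as a total, names baseline as one of its times and offers no exclusion, so a programmer following it would include the baseline screen. It is also fair that under the null the ratio is 1 at every time. The model then holds and the test is valid, so the cost arises only when there is an effect.

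Several stronger readings are tempting, and the document does not support them.

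- **The plan scores missed screens as negative.** It nowhere says so. This is a consequence of the count when no at-risk rule is given, and such a rule may sit in a statistical analysis plan not shown here.
- **The 30–50% attrition in Section 10.6 will distort the result.** Those figures concern dropout: 30% is assumed, and 50% is a sensitivity value prompted by another study's follow-up rate. Censoring handles dropout without bias when it is unrelated to use. The protocol gives no rate for intermittent misses, and none by arm.
- **The unadjusted model is invalid.** A randomised comparison with arm alone and a robust variance is valid. Omitting site, court mandate and baseline result costs efficiency only.
- **Urine is the sole objective check on the primary outcome, so it must be stimulant-only.** A breathalyzer is used at the same visits (Section 5.4.3.1.2). Section 5.4.3.1.1 declines to treat urine as a gold standard. The screen covers several classes ("urine will be tested for the presence of cocaine, opiates, cannabis, benzodiazepines, methamphetamines, and amphetamines"), and the governing objective in Section 10.4.1.1 concerns non-stimulant drugs. An any-drug endpoint is a design choice.
- **The same fault affects meeting attendance.** Section 10.4.4.1.5 plans an analysis "using the proportional mean model for recurrent events similar to the model for mean number of positive drug screens", but it compares client subtypes, not randomised arms. The argument that treatment cannot affect baseline does not carry over.

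**Conclusion.** The point holds in two parts of unequal weight.

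The baseline part rests on the text. Counting a pre-randomisation screen under a single treatment ratio dilutes a real effect: 0.67 to 0.75 in the worked example, and 0.70 to between 0.75 and 0.84 over the assumed range. In the central case it costs about 17 percentage points of power (86% to 69%). It does not create false positives. These sizes depend on assumed positivity rates and on complete data.

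The missed-screen part is conditional. It needs intermittent misses that differ between arms, or dropouts left in the risk set. Where that happens the bias can be substantial and favours the arm with more misses. With equal missingness, or censored dropout unrelated to use, there is none.

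The endpoint is fifth in priority and exploratory, so the impact is moderate. The section should be corrected, but the primary conclusion does not depend on it.

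**What to change.** Amend Section 10.4.1.1.2 as follows.

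1. Restrict the outcome to the post-randomisation screens at weeks 4 and 8 and months 3 and 6.
2. Enter the baseline screen result and the randomisation strata (site, court mandate) as covariates. The strata are for efficiency and for consistency with the primary model.
3. Count a participant as at risk only at screens actually taken, and state the censoring rule. This can be done within the planned model or by a repeated-measures logistic model of attended screens. Either version still assumes that a missed screen is uninformative given what is modelled, and the text should say so.
4. Add one sensitivity run with missing scored as positive. It leans the opposite way: with 30% true positivity in both arms and 10% against 30% missed, it gives (0.30 × 0.70 + 0.30)/(0.30 × 0.90 + 0.10) = 0.51/0.37 = 1.38. It should be read as a bound, not a correction.

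Reporting stimulant-positive screens beside the any-drug result is optional.

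In simulation, dropping baseline and using screens taken as the risk set recovered the true 0.70. The cost is a change of wording and programming, with no new data, visits or sample size.
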